4.1. Protocol Deviations

- Important protocol deviations (including deviations related to study inclusion/exclusion criteria, conduct of the trial, subject management or subject assessment) will be summarised and listed.
- Important deviations which result in exclusion from the PP population will also be summarised and listed. (Please refer to Appendix 1: Protocol Deviation Management and Definitions for Per Protocol Population).
 - Protocol deviations will be tracked by the study team throughout the conduct of the study in accordance with the Protocol Deviation Management Plan.
 - Data will be reviewed prior to releasing the randomization codes and freezing the database to ensure all important deviations and deviations which may lead to exclusion from the PP analysis are captured and categorised on the protocol deviations dataset.
 - This dataset will be the basis for the summaries and listings of protocol deviations.
- A separate summary and listing of all inclusion/exclusion criteria deviations will also be provided. This summary will be based on data as recorded on the inclusion/exclusion page of the eCRF.
- A listing of any treatment misallocations will be produced for the ASE population.

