6.4. Blinding

This is an open label study with no blinding of IP due to lack of availability of placebo Respimat.

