9.2. Sample Size Considerations

9.2.1. Sample Size Assumptions

The sample size calculations use a one-sided 2.5% significance level and an estimate of within-subject standard deviation (SD) for trough FEV_1 of 140 ml. The estimate of SD is based on a mixed model repeated measures (MMRM) analyses of two previous cross-over studies in COPD subjects evaluating trough FEV_1 at Week 2. The observed SD from these studies (133ml in DB2116132 and 113ml in DB2116133) has been increased to allow for additional variability that may be observed during an 8 week treatment period.

A study with 168 evaluable subjects for the primary analysis on the per-protocol (PP) population will have 90% power to detect non-inferiority of UMEC/VI to TIO/OLO based on trough FEV_1 at Week 8, when the margin of non-inferiority is -50mL and the true mean treatment difference is assumed to be 0mL.

It is estimated that approximately 10% of subjects who will provide a Week 8 assessment will be excluded from the PP population, which would require 186 subjects with a Week 8 assessment in the ITT population. Allowing for a 15% withdrawal rate, a total of 220 subjects will be randomised.

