9.2.2. Sample Size Sensitivity

The within-subject SD of 140 ml for trough FEV₁ used for the sample size calculations was based on two previous cross-over responder studies in COPD subjects evaluating trough FEV₁ at Week 2. If the standard deviation observed in this study is different from the estimated value used in the sample size calculation, the power to determine non-inferiority based on trough FEV₁ at Week 8 will be affected. Table 4 illustrates the power which would be obtained with various standard deviations, assuming the number of evaluable subjects remains constant at 168 and the non-inferiority margin is -50 mL.

Within-subject SD (mL)	Power for Margin of -50 mL
100	>99%
120	97%
140	90%
160	81%
180	72%

Table 4Impact on Power of Different Estimates of Standard Deviation for
Trough FEV1

If the within subject SD increased to 180 mL, the study would have 72% power to conclude non-inferiority based on a margin of -50 mL. If the SD were 100 mL then the study would have >99% power to conclude non-inferiority.

Based on a within subject SD of 140 mL and a sample size of 168 evaluable PP subjects, the lower confidence bound for the treatment difference would be greater than 0 at an observed treatment difference of 30 mL [detectable effect].

Based on a within subject SD of 140 mL and a sample size of 186 ITT subjects, the study would conclude superiority (i.e. lower confidence bound > 0) with a treatment difference of 29mL [detectable effect].

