1. REPORTING & ANALYSIS PLAN SYNPOSIS

Overview	Key Elements of the RAP
Purpose	 This RAP details all planned analyses and outputs required for the final Clinical Study Report (CSR) of study 204990.
Protocol	This RAP is based on the original protocol (Dated: 29-Mar-2016) for study 204990 [GlaxoSmithKline Document Number 2015N256437_00] and eCRF Version 1.2.
Primary Objective	 To compare the effect of UMEC/VI 62.5/25mcg with TIO/OLO 5/5mcg once daily on lung function in subjects with moderate COPD over 8 weeks of treatment.
Primary Endpoint	Trough FEV1 at Week 8
Study Design	 Multicentre, randomized, open-label, 2 period cross-over, complete block design study to evaluate the efficacy and safety of UMEC/VI 62.5/25mcg with TIO/OLO 5/5mcg when used in subjects with moderate COPD.
	• Eligible subjects will be randomized to receive a sequence consisting of UMEC/VI 62.5/25 mcg once-daily administered as 1 inhalation once-daily from the Ellipta Inhaler and TIO/OLO 5/5mcg inhalation spray administered as inhalation of 2 puffs once-daily from the Respimat inhaler. Each treatment period will be 8 weeks.
	 A study with 168 evaluable subjects for the primary analysis on the per-protocol (PP) population will have 90% power to detect non-inferiority of UMEC/VI 62.5/25mcg to TIO/OLO 5/5mcg based on trough FEV₁ at Week 8, when the margin of non-inferiority is -50mL and the true mean treatment difference is assumed to be 0mL.
	Based on 15% withdrawal rate and 10% exclusion rate from the PP population 220 subjects will be randomized.
Planned	No interim analyses are planned.
Analyses	 All decisions regarding final analysis, as defined in this RAP document, will be made prior to Database Freeze (unblinding) of the study data.
Analysis Populations	 The All Subjects Enrolled Population will comprise all subjects for whom a record exists on the study database, including screen failures and any subject who was not screened but experienced a serious adverse event (SAE) between the date of informed consent and the planned date of the Screening Visit. This population will be used for reporting subject disposition, reasons for withdrawal prior to randomization, and inclusion, exclusion and randomization criteria deviations and SAEs for non-randomized subjects.

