10.1. Appendix 1: Protocol Deviation Management and Definitions for Per Protocol Population

10.1.1. Exclusions from Per Protocol Analysis

The full list of protocol deviations collected on the eCRF is in the PDMP. This will include those that will also be excluded from the per protocol analyses.

Concomitant medications will be reviewed for deviations from the time of informed consent through to the time of stopping study treatment.

Subjects with partial deviations will be excluded from PP analyses from the onset of the deviation onwards. Subjects with time point specific or period specific deviations will have only the affected time point excluded from PP analyses.

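### Deciding per-protocol exclusions before code release is the only stated control on what reviewers know, and it is weak in an open-label trial

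*SAP*

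**What the plan says.** Protocol 6.4 leaves treatment open: "This is an open label study with no blinding of IP due to lack of availability of placebo Respimat".

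Protocol 9.3.1 and SAP 1 make the PP set the primary population for non-inferiority and, if that is shown, for superiority. Exclusion is graded: whole subject, from a time point onwards, one period, or one visit.

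The control on these decisions is timing. SAP 4.1 states: "Data will be reviewed prior to releasing the randomization codes and freezing the database". SAP 3.1 and the PP definition in SAP 4 give the same order. SAP 1 says that decisions about the final analysis "will be made prior to Database Freeze (unblinding) of the study data".

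Protocol 9.3.1 promised that the RAP would define the grades of deviation, and SAP 4 says Appendix 1 defines them. Appendix 1 (SAP 10.1.1) lists no criteria and refers elsewhere: "The full list of protocol deviations collected on the eCRF is in the PDMP".

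A few rules are explicit: taking the wrong treatment is a full deviation (Protocol 9.3.1, SAP 1), troughs outside 22.0-25.0 h are dropped from PP (Protocol 7.3.1, SAP 10.3.1), and so are values taken after that day's dose (SAP 10.6.4).

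**The concern.** Holding back codes masks a review only if treatment cannot be learned another way. Here it can. The compliance data in SAP 10.6.2 are counts from a 30-dose Ellipta or a 60-inhalation Respimat, and the error checklists in SAP 10.6.4 differ by device. In a two-period crossover, knowing the device in one period gives the treatment in both. Under SAP 3.1, exclusions are agreed after all subjects have finished and the data are cleaned, so the FEV1 results already exist. Neither document says that the reviewers are kept from treatment or outcome.

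Classification needs judgement wherever a deviation must be rated for its effect on efficacy, and dropping one period drops one treatment's data. If that judgement leans on the outcome, even unintentionally, the estimate that decides the trial moves. The PP interval alone decides non-inferiority.

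**Working it through.** **Inputs from the documents**
- Protocol 9.2.1: "The sample size calculations use a one-sided 2.5% significance level". The power statement applies "when the margin of non-inferiority is -50mL and the true mean treatment difference is assumed to be 0mL".
- Protocol 9.2.2: "Based on a within subject SD of 140 mL and a sample size of 168 evaluable PP subjects".
- Protocol 9.2.1: about 10% of subjects with a Week 8 value are excluded from PP (186 in ITT, 168 in PP).

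**The plan's own figure.** Protocol 9.2.1 says the study "will have 90% power to detect non-inferiority of UMEC/VI to TIO/OLO".
- SE = 140 x sqrt(2/168) = 15.3 mL.
- Normal approximation: power = Phi(50/15.3 - 1.96) = 90.5%. Noncentral t on 166 df: 90.2%.
- The stated 90% is reproduced, so 15.3 mL is the right yardstick.

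**Effect of selective exclusion (illustration).** Let R be the mean UMEC/VI minus TIO/OLO difference in retained subjects, and let excluded subjects have mean R - d.
- Mean over all subjects = 0.90R + 0.10(R - d) = R - 0.10d.
- The PP estimate therefore exceeds the all-subject estimate by 0.10d.

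| d, assumed (mL) | Shift 0.10d (mL) | Share of 50 mL margin | In SE |
|---|---|---|---|
| 50 | 5 | 10% | 0.33 |
| 100 | 10 | 20% | 0.65 |
| 150 | 15 | 30% | 0.98 |

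**With the plan's counts.** 186 - 168 = 18 excluded, and 18/186 = 9.7%. The shifts are 4.8, 9.7 and 14.5 mL.

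**Effect on false non-inferiority.** If the all-subject difference is truly -50 mL, the chance of declaring non-inferiority on PP is 1 - Phi(1.96 - shift/15.3). For these three shifts it is 5.0%, 9.2% and 15.6%, against a nominal 2.5%.

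The values of d are assumptions; the documents give none. The model removes whole subjects in one direction. Selection the other way would lower the estimate, and period- or visit-level exclusion would act differently because the subject's other data stay in the model.

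**The case against.** A reader might infer that code-release timing is the plan's only safeguard and that it protects nothing. The documents do not support that.
- SAP 7.1.1 repeats every primary-endpoint output on ITT, which keeps deviators, and calls for further investigation if PP and ITT disagree.
- The 22.0-25.0 h window is a numerical rule that leaves little discretion.
- Exclusions must follow the PDMP (SAP 3.1), deviations are tracked during the study, and exclusions are summarised and listed (SAP 4.1).
- Spirometry testers are blinded to treatment (Protocol 4.4).
- Withholding codes still delays the formal analysis by treatment until exclusions are settled.

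It is also not documented that reviewers have treatment and FEV1 in front of them. The documents do not say who reviews or what they see, and the PDMP may hold firm criteria.

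A larger shift is also tempting: 0.10/0.90 of d gives 5.6, 11.1 and 16.7 mL. That factor applies only when d is measured from the mean of all subjects, not from the retained ones. Moreover, the calculated shift is a gap between PP and all subjects, which a fully masked removal of genuine deviators could also produce. It is not an estimate of bias from unmasked review.

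These points narrow the concern but do not remove it. The ITT repeat is described as a superiority test (Protocol 9.4.1, SAP 1), and the further investigation has no criterion or consequence. The tipping-point analysis addresses missing data, not who was classed as a deviator. Blinded testers protect the measurement, not the later classification. Listings expose a problem after the fact. PDMP criteria would reduce discretion but would not by themselves mask the people applying them.

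**Conclusion.** The concern holds in a limited form. Timing before code release is the only stated control on what reviewers know when they classify PP exclusions. In an open-label trial it is weak, because ordinary trial data reveal the device. The other safeguards mitigate or expose selective exclusion without preventing it, and non-inferiority is decided on PP.

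With 10% excluded and an assumed shortfall of 50-150 mL against retained subjects, the PP estimate would move by about 5-15 mL: less than a third of the margin and no more than about one SE. This shows sensitivity. It is not evidence that exclusions were or will be selective. The conclusion also depends on the PDMP, which is outside these documents; if it already masks classification, only the SAP wording needs to change.

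**What to change.** Amend SAP 4.1 and Appendix 1 as follows.
- Classify subject-, period- and visit-level PP exclusions from listings with device, sequence, treatment and post-baseline spirometry values removed.
- Show compliance only as a percentage. SAP 10.6.2 already puts both inhalers on that scale, so the device need not appear.
- Show spirometry only as timing relative to dose, which is enough to apply the 22.0-25.0 h rule.
- Handle wrong-treatment deviations separately by the fixed rule already stated, since they require comparing randomised with actual treatment.
- Sign and date the exclusion list before any FEV1 summary by treatment is produced.

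This is a cheap improvement. The review is already planned, and no visit, sample size, model or additional staff is involved. The downside is some programming time to prepare the masked listings.

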5. CONSIDERATIONS FOR DATA ANALYSES AND DATA HANDLING CONVENTIONS

Table 2 provides an overview of appendices within the RAP for outlining general considerations for data analyses and data handling conventions.

Section	Component
10.1	Appendix 1: Protocol Deviation Management and Definitions for Per Protocol Population
10.2	Appendix 2: Time & Events
10.3	Appendix 3: Assessment Windows
10.4	Appendix 4: Treatment States and Phases
10.5	Appendix 5: Data Display Standards & Handling Conventions
10.6	Appendix 6: Derived and Transformed Data
10.7	Appendix 7: Premature Withdrawals & Handling of Missing Data
10.8	Appendix 8: Multicenter Studies
10.9	Appendix 9: Examination of Covariates, Subgroups & Other Strata
10.10	Appendix 10: Multiple Comparisons & Multiplicity
10.11	Appendix 11: Model Checking and Diagnostics for Statistical Analyses.

Table 2Overview of Appendices

6. STUDY POPULATION ANALYSES

6.1. Overview of Planned Analyses

The study population analyses will be based on the ITT population, unless otherwise specified.

Table 3 provides an overview of the planned study population analyses, with full details of data displays being presented in Appendix 13: List of Data Displays.

Table 3Overview of Planned Study Population Analyses

Display Type	Data Displays Generated		
	Table	Figure	Listing
Subject Disposition			
Study Populations and Reasons for Screen Failures (ASE)	Y		
Attendance at Each Clinic Visit	Y		
End of Study Record	Y		Y
Treatment Completion	Y		
Reasons for Subject Withdrawal from the Study During	v		
Each Period	1		
Reasons for Discontinuation of Treatment During Each	v		
Period	1		
Number of Subjects by Country and Centre	Y		
Follow-up Contact			Y
Treatment			
Randomized and Actual Treatments			Y
Overall Percentage Treatment Compliance	Y		Y
Subjects Who Discontinued Study Treatment			Y
Protocol Deviations	1	T	
Important Protocol Deviations	Y		Y
Exclusions from Per Protocol Analyses	Y		Y
Inclusion/Exclusion/Randomization Criteria Deviations,	Y		Y
ASE and ITT	ľ		•
Treatment Misallocations (ASE)			Y
Demography	1		
Demographic Characteristics, ITT and PP (Note the listing	Y		Y
will only be produced for ITT)			•
Race and Racial Combinations	Y		
Race and Racial Combinations Details	Y		Y
Age group breakdown for the trial (ASE)	Y		
Subject Number per Country (ASE)	Y		
Medical Conditions and Concomitant Medications			
Current/Past Medical Conditions	Y		Y
Family History of Cardiovascular Risk Factors	Y		Y
COPD Concomitant Medications Not Given for an			
Exacerbation (Pre-Run-in, During Run-in or Washout, On-	Y		Y
treatment, Post-treatment) (Only one listing required for all			-
COPD medications)			

Display Type	Data Displays Generated			
	Table	Figure	Listing	
COPD Concomitant Medications Given for an Exacerbation	Y		Y	
(On-treatment, During Washout, Post-treatment)				
treatment) (Only one listing required for all non-COPD medications)	Y		Y	
Relationship Between Anatomical Therapeutic				
Classification (ATC) Level 1, Ingredient and Verbatim Text			Y	
Non-COPD Concomitant Medications Only				
Disease and Background Characteristics				
COPD History and COPD Exacerbation History (only one listing required)	Y		Y	
Smoking History and Status	Y		Y	
Screening Lung Function Test Results (listed as part of the Listing of FEV1)	Y		Y	
GOLD Categories and Reversibility at Screening	Y		Y	
Screening IC Results (listed as part of the Listing of IC)	Y		Y	
mMRC Dyspnoea Scale at Screening	Y		Y	

NOTES :

• Y = Yes display generated.

6.1.1. Subject Disposition

The number of subjects in the ASE population, the number and percentage of subjects who were pre-screen failures, who had exacerbations during the pre-screening period, who attended the screening visit and of those the number and percentage of subjects who were screen failures with the reasons for failing or run-in failures with reasons for failing will be presented. The number of subjects randomized and the number of subjects who were in the ITT population will be presented by treatment and overall. Of those in the ITT population the number and percentage of subjects who discontinued treatment and the number and percentage of subjects in the PP Population will be presented by treatment and overall.

The number and percentage of subjects who completed the study as planned as well subjects who stopped investigational product prematurely will be presented, along with the number and percentage of subjects who reported each primary and sub-reason for discontinuation of treatment.

The end of study record summary shows the number of subjects who completed the study as well as the number who withdrew early from the study along with reasons for early withdrawal.

A summary of the number and percentage of subjects who entered, discontinued treatment and completed each period of the study will be displayed.

A summary of reasons for withdrawal during each period (period 1, washout and period 2) will be presented for each treatment. A summary of reasons for discontinuation of treatment during each period will also be produced.

6.1.2. Medical Conditions and Concomitant Medications

The number and percentage of subjects reporting each current medical condition will be presented for the overall population. This table will include a category of 'Any Cardiovascular Risk Factor' and will present all medical conditions regardless of frequency. The table will be repeated for past medical conditions.

Non-COPD medications will be summarised by Anatomical-Therapeutic-Chemical (ATC) level 1 and ingredient. Multi-ingredient medications will be presented according to their combination ATC classification rather than the classifications of the ingredients.

Respiratory Medication Class (RMC) will be provided by Data Management for each COPD concomitant medication. COPD medications not given for an exacerbation, and medications given for an exacerbation, will be summarised by Respiratory Medication Class (RMC).

COPD and non-COPD medications will be listed separately. The COPD medications listing will indicate whether each medication was taken for an exacerbation. Both listings will indicate in which treatment state each medication was taken (Pre-Run-in, During Run-in, On-treatment, During Washout, Post-treatment).

A listing of the relationship between ATC Level 1, ingredient and verbatim text will be produced for non-COPD medications only.

6.1.3. Disease and Background Characteristics

Pre- and post-salbutamol FEV₁, FVC and FEV₁/FVC ratio, post-salbutamol FEV₁ as a percentage of predicted normal and FEV₁ reversibility to salbutamol (expressed in mL and as a percentage) at Screening will be summarised by treatment and overall.

The number and percentage of subjects in each GOLD Grade 1-4, GOLD Category A-D using mMRC and GOLD Category A-D using CAT, and the number and percentage of subjects classified as Reversible/Non-reversible to salbutamol at Screening (defined in Section 10.6.2) will also be summarised by treatment and overall.

History of disease, along with smoking status and family history of cardiovascular disease will also be summarised by treatment and overall.

7. PRIMARY STATISTICAL ANALYSES

7.1. Efficacy Analyses

7.1.1. Overview of Planned Efficacy Analyses

The primary efficacy analyses for the primary endpoint will be on the PP population. All outputs produced for the primary endpoint will be repeated on the ITT population. Further investigation will be done if the results from the PP analysis are not consistent with the results from the ITT analysis for the primary endpoint. In addition, a tipping point analysis will be carried out as a sensitivity analysis for the primary endpoint of trough FEV₁ at Week 8 on the PP and ITT population in order to assess the impact of missing data on conclusions of non-inferiority and superiority.

Table 4 provides an overview of the planned efficacy analyses for the primary endpoint, with full details of data displays being presented in Appendix 13: List of Data Displays.

Table 4 Overview of Planned Efficacy Analyses for the Primary Endpoint

Endpoint	Change from Baseline [1]						
	Stats Analysis Summary Ind			Indiv	ridual		
	Т	F	L	Т	F	F	L
Trough FEV ₁							
Trough FEV ₁ at Week	Y	Y3		Y	Y2		Y
8 (ITT and PP							
population)							
Tipping point on	Y						
Trough FEV ₁ at Week							
8 (ITT and PP							
population)							

NOTES :

- T = Table, F = Figure, L = Listing, Y = Yes display generated.
- Stats Analysis = Represents TFL related to any formal statistical analyses (i.e. modelling) conducted.
- Summary = Represents TFL related to any summaries (i.e. descriptive statistics) of the observed raw data.
- Individual = Represents FL related to any displays of individual subject observed raw data.
- [1] Analysis and Summaries to include absolute values too.
- ² Box plot and empirical distribution function plot for change from baseline.
- ³ Figures include all time points produced for change from baseline only.

7.1.2. Planned Efficacy Statistical Analyses

Primary Statistical Analyses					
Endpoint(s)					
 Trough FEV₁ at Week 8 (results for trough FEV₁ at Week 4 will be obtained from the same analysis) 					
Model Specification					
 Trough FEV₁ at Week 8 will be analysed for the PP population using a mixed model repeated measures (MMRM) including data recorded at each of Week 4 and Week 8. The following covariates will be included in the model: period baseline (the difference between a subject's baseline in each treatment period and the mean overall baseline for that subject), mean baseline (the mean of the baselines in each of the two treatment periods), period, treatment, visit, visit by period baseline, visit by mean baseline and visit by treatment interactions, where visit is nominal Subject will be fitted as a random effect. Two models will be fitted; one with a response variable of trough FEV₁, and one with a response variable of change from baseline in trough FEV₁. An unstructured covariance structure for the R matrix will be used by specifying 'type=UN' on 					
the REPEATED line.					
• The Kenward and Roger method for approximating the denominator degrees of freedom and correcting for bias in the estimated variance-covariance of the fixed effects will be used. If this method does not run, the residual method will be used instead.					
Example SAS code					
proc mixed data=start; class subject period treatment visit; model endpoint=period treatment visit mean_base period_base visit*period_base visit*mean_base visit*treatment / ddfm=kr; random intercept / subject=subject; repeated visit / subject=subject*period type=un; Ismeans visit*treatment / cl diff e; ods output Ismeans=Ismeans; ods output diffs=diffs; run;					
Model Checking & Diagnostics					
Refer to Appendix 11: Model Checking and Diagnostics for Statistical Analyses.					
Model Results Presentation					
 Least squares (LS) mean and LS mean changes from baseline with their corresponding standard errors (SEs) will be presented for each treatment by visit, together with estimated treatment differences (UMEC/VI 62.5/25 vs. TIO/OLO 5/5), corresponding 95% CIs and p-values. A plot of LS mean changes from baseline and 95% CIs for each treatment by visit will be generated 					
 The type III tests of fixed effects and the covariance parameter estimates from the model will be presented in two tables. 					

Summary Results Presentation

• Summary of baseline FEV₁ will be presented by treatment for all subjects.

Primary Statistical Analyses

- A box plot and an empirical distribution function plot of change from baseline in trough FEV₁ at Week 8 will be produced.
- Summary statistics for raw and change from baseline in trough FEV₁ at each visit and for each treatment will be presented on the same table.

Sensitivity and Supportive Statistical Analyses

- The analysis and results presentation will be repeated for the ITT population (with the exception of the box plot and empirical distribution function plot).
- Sensitivity of the results to missing data will be assessed using Tipping Point Analysis for both the PP and ITT population. Analysis of the primary endpoint at Week 8 will be run with missing data imputed under a variety of assumptions for the mean of the missing data. This will be done for both study arms separately. These analyses will allow for determination of the 'tipping point(s)' which is, the mean values for missing data that would cause a change in the conclusion of a)non-inferiority and b)superiority as assessed by the lower limit of the two-sided 95% CI. Multiple- imputation will be used for imputing the Week 8 endpoint of interest for subjects who had missing on-treatment data at Week 8.

For each imputation, a random draw will be made from a normal distribution with mean equal to the corresponding assumed mean change from baseline and standard deviation taken from the observed change from baseline data for the combined treatment arms at the Week 8 visit. Data for subjects with missing baseline values will not be imputed. Analysis of the complete Week 8 dataset will be carried out using an ANCOVA model with covariates of treatment group and baseline for that particular period (Note: not the period baseline).

Initially the same mean change from baseline will be assumed for subjects who withdrew from both treatment arms. The assumed values for the mean change from baseline at Week 8 will vary from -150mL to +150mL in increments of 50mL.

The analysis will be repeated assuming different mean changes from baseline for subjects who withdrew from each treatment arm. For each value of the assumed mean change from baseline for subjects who withdrew from UMEC/VI, the full range of values for subjects who withdrew from TIO/OLO will be investigated.

Seeds for multiple imputation analyses will be set using the following SAS code:

```
data seed1;
   number=round(10000*ranuni(0),1);
   output;
run;
```

proc print; run;

The seeds generated and assigned to each analysis will be documented separately prior to DBF. A table will be produced displaying the two-sided 95% lower confidence limit of the Week

Sensitivity and Supportive Statistical Analyses

8 treatment differences under the above assumptions for the mean changes from baseline for each of the treatment arms

• An assessment of whether the effect of treatment is modified by the interaction of

Period

Period baseline

Mean baseline

will be made. Interactions with treatment will be investigated by fitting separate MMRM models with the same terms as the main model, and adding in treatment by factor by visit interaction. Contrast statements will be used to obtain the p-value for the treatment by factor interaction at Week 8. The interaction term will be tested at the 10% significance level. If that p-value is >=0.10 the interaction will be considered not significant. If the p-value is <0.10, further investigation will be performed, for example running analysis by each level of the factor, or for subgroups above and below the median. This will be assessed for the PP population.

